14-Day Patient Albuterol Use: 14-day patient albuterol use is each patient’s total number of albuterol inhalations taken and the number of days used during the first 14 days (study day 1 through study day 14) of study participation with an indicator of whether or not the most frequent daily usage of albuterol is in one of the following 3 categories: (1) 0 to 2 inhalations, (2) 3-6 inhalations and (3) > 6 inhalations. It is presented as “D14:I#iD#dMTN#n”, where “i” is the number of albuterol inhalations and “d” is the number of days used in the first 14 days of study, and “n” is an indicator of whether or not the most frequent daily usage of albuterol is in one of the 3 categories. If there is a tie in the most frequent daily usage, the category with the highest number of inhalations will be reported.

Albuterol use will be examined by the following 3 parameters; (i) total number of inhalations in the days preceding the peak of a CE-COPD, (ii) number of days prior to the peak of a CE-COPD when albuterol use increased, and (iii) number of albuterol uses in the day preceding a CE-COPD.

The maximum number of inhalations taken within a 24-hour period by each patient: The date and time stamp of the inhalations are taken into consideration when determining the maximum number of inhalations taken within a 24-hour period by each patient. For patients who experienced a CE-COPD, the maximum number of inhalations taken within a 24-hour period is determined among the days prior to the date of the symptom peak of the exacerbation.

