7.1.2.3. Hypothesis: Albuterol Use Will Increase Several Days Prior to a CE-COPD

The hypothesis under consideration is that albuterol use will increase several days prior to a CE-COPD. Several days will be defined as 7 days prior to the date of the CE-COPD symptom peak for this analysis.

For each subject that experiences at least 1 CE-COPD, Y_1, \dots, Y_7 will represent the number of puffs of albuterol during the 7 days preceding the date of the CE-COPD symptom peak and Y_8, \dots, Y_{14} will represent the number of puffs taken each day during days 8 through 14 preceding the date of the CE-COPD symptom peak. Under the hypothesis of no increased albuterol use

preceding an exacerbation (ie, null hypothesis) assume for subject "xxx" that $Y_i \stackrel{iid}{\sim} \text{Poisson}(\lambda_{xxx})$ for all subjects i. Alternatively, if albuterol use does increase prior to an exacerbation, then

$Y_i \stackrel{iid}{\sim} \text{Poisson}(\lambda_{xxx})$ during day 8 through 14 preceding the date of the CE-COPD symptom peak

and $Y_i \stackrel{iid}{\sim} \text{Poisson}(\lambda_{xxx} + \delta)$ for the immediate 7 days preceding the CE-COPD(s). Also, for random subject effect, assume λ_{xxx} follows some distribution to account for subject to subject variability. Let d_{xxx} will equal to the mean number of puffs during the 7 days immediately preceding the date of the CE-COPD symptom peak minus mean number of puffs during days 8 through 14 preceding the date of the CE-COPD symptom peak. To assess if albuterol usage increases 7 days prior to a CE-COPD, $H_0: \mu_D = 0$, $H_1: \mu_D > 0$ will be tested using a t-test at the 0.05 significance level.

7.1.2.4. Number of Days Prior to the Peak of a CE-COPD When Albuterol Use Increased

Among patients who experienced a CE-COPD, summary statistics of the number of days prior to the peak of a CE-COPD when albuterol use increased, will be presented overall and by moderate CE-COPDs and severe CE-COPDs for 3 thresholds defining an increase in albuterol use;

- (i) First occurrence of a single day increase of 20% from baseline use prior to CE-COPD
- (ii) First occurrence of a single day absolute increase of 2 inhalations from baseline use prior to CE-COPD
- (iii) First occurrence of a single day absolute increase of 4 inhalations from baseline use prior to CE-COPD

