Among patients who did not experience a CE-COPD, summary statistics, including 95% CIs intervals of the proportion of eMDPI time on study days when a patient exceeded a given threshold of albuterol use (number of days a given patient's single day's albuterol use exceeded 4 inhalations/total number of eMDPI study days for a given patient), will be summarized for 3 thresholds defining an increase in albuterol use;

- (i) First occurrence of a single day increase of 20% from baseline use
- (ii) First occurrence of a single day absolute increase of 2 inhalations from baseline use
- (iii) First occurrence of a single day absolute increase of 4 inhalations from baseline use

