7.1.2.5. Maximum Number of Inhalations Taken In a 24-Hour Period

Summary descriptive statistics of the maximum number of inhalations taken in a 24-hour period will be presented overall and by CE-COPD status and by CE-COPD severity.

Data listings for each parameter of albuterol use will be presented by patient.

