7.2.2. Analysis Methods for Inhalational Flow Values

7.2.2.1. Actual and Change from Baseline in Study Day X Inhalational Flow Values Prior to the Peak of a CE-COPD

Among patients who experienced a CE-COPD, summary descriptive statistics of the actual inhalational flow values and change from baseline in daily inhalational flow values for MIF, inhalational volume, inhalation duration, and time to MIF at 1 day (eg, the 24-hour period on the day prior to the date of the CE-COPD symptom peak) and at 3, 5, 7, 10, 14, and 21 days preceding the peak of a CE-COPD, will be presented for all CE-COPDs and by moderate CE-COPDs and severe CE-COPDs.

In this analysis, among patients experiencing more than 1 CE-COPD, the subsequent CE-COPDs will be considered a separate CE-COPD distinct from the first (preceding) CE-COPD, provided the patient exhibited at least 1 day of baseline albuterol use after the first (preceding) CE-COPD’s date of symptom peak and prior to the subsequent CE-COPD’s date of symptom peak. For patients who experience multiple CE-COPDs (eg, 3), for a given number of days preceding a CE-COPD (eg, 7 days), if the (eg, third) CE-COPD overlaps with the time period of the preceding (eg, second) CE-COPD, the CE-COPD (eg, third CE-COPD) should not be included in the analysis.

Summary descriptive statistics of the actual inhalational flow values and change from baseline in daily inhalational flow values for MIF, inhalational volume, inhalation duration, and time to MIF will be presented for overall, by CE-COPD status, by CE-COPD severity (Yes: severe, moderate; No) and for the first occurrence of a single day increase of 20% from baseline use. For patients who experienced a CE-COPD, the single day increase of 20% from baseline use is the single day increase of 20% from baseline use prior to the exacerbation.

In addition, summary descriptive statistics of the maximum change from baseline in daily inhalational flow values for MIF, inhalational volume, inhalation duration, and time to MIF, will be presented overall and by CE-COPD status and by CE-COPD severity (Yes: severe, moderate; No). For patients who experienced a CE-COPD, the maximum change from baseline is the maximum change prior to the exacerbation.

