7.3.2. Analysis Methods for Total Daily Steps

7.3.2.1. Actual and Change from Baseline in Study Day X Total Daily Steps Prior to the Peak of a CE-COPD

Among patients in the ankle accelerometry cohort who experienced a CE-COPD, summary descriptive statistics of the actual TDS and change from baseline in TDS 1 day (eg, the 24-hour period on the day prior to the date of the CE-COPD symptom peak) and at 3, 5, 7, 10, 14, and 21 days preceding the peak of a CE-COPD, will be presented for all CE-COPDs and by moderate CE-COPDs and severe CE-COPDs.

In this analysis, among patients experiencing more than 1 CE-COPD, the subsequent CE-COPDs will be considered a separate CE-COPD distinct from the first (preceding) CE-COPD provided the patient exhibited at least 1 day of baseline albuterol use after the first (preceding) CE-COPD's date of symptom peak and prior to the subsequent CE-COPD's date of symptom peak. For patients who experience multiple CE-COPDs (eg, 3), for a given number of days preceding a CE-COPD (eg, 7 days), if the (eg, third) CE-COPD overlaps with the time period of the preceding (eg, second) CE-COPD, the CE-COPD (eg, third CE-COPD) will not be included in the analysis.

Among patients in the ankle accelerometry cohort, summary descriptive statistics of the actual TDS and change from baseline in TDS, will be presented for overall, by CE-COPD status, by CE-COPD severity (Yes: severe, moderate; No) and for the first occurrence of a single day increase of 20% from baseline use. For patients who experienced a CE-COPD, the single day increase of 20% from baseline use is defined as the single day increase of 20% from baseline use prior to the exacerbation.

In addition, summary descriptive statistics of the maximum change from baseline in TDS will be presented overall and by CE-COPD status and by CE-COPD severity. For patients who experienced a CE-COPD, the maximum change from baseline in TDS is the maximum change from baseline in TDS during the days prior to the exacerbation.

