7.4.2. Analysis Methods for Sleep Disruption Indices

7.4.2.1. Actual and Change from Baseline in Study Day X Sleep Disruption Indices Prior to the Peak of a CE-COPD

Among patients in the wrist accelerometry cohort who experienced a CE-COPD, summary descriptive statistics of nighttime average sleep latency time, longest nighttime wake episode, and total time awake at night and change from baseline in these 3 measures of SDI at 1 day (eg, the 24-hour period on the day prior to the date of the CE-COPD symptom peak) and at 3, 5, 7, 10, 14 and 21 days preceding the peak of a CE-COPD, will be presented for all CE-COPDs and by moderate CE-COPDs and severe CE-COPDs.

Summary descriptive statistics of nighttime average sleep latency time, longest nighttime wake episode, and total time awake at night and change from baseline in these 3 measures of SDI will be presented for overall, by CE-COPD status, by CE-COPD severity (Yes: severe, moderate; No) and for the first occurrence of a single day increase of 20% from baseline use. For patients who experienced a CE-COPD, the single day increase of 20% from baseline use is defined as the increase prior to the exacerbation.

In addition, summary descriptive statistics of the maximum daily change from baseline nighttime average sleep latency time, longest nighttime wake episode, and total time awake at night, will be presented overall and by CE-COPD status and by CE-COPD severity. For patients who experienced a CE-COPD, the maximum daily change from baseline is the change prior to the exacerbation.

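### Lead time is dated from the first-ever single-day crossing with no look-back limit, so at 20% it mainly reflects the study day of the peak unless use is very regular; maxima are cut at the event only in CE-COPD patients

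*SAP*

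**What the plan says.** The timing of the rise before the peak is one of three albuterol parameters named in SAP 1.1 and Protocol 2.1. SAP 7.1.2.4 defines it by three thresholds relative to baseline: "First occurrence of a single day increase of 20% from baseline use prior to CE-COPD", and the same rule for absolute rises of 2 and 4 inhalations. Baseline is the mean of study days 1 to 7, and patients with a CE-COPD in that week are excluded (SAP 7.1.1). The section does not say how far back the search may go, whether it starts on day 1 or day 8, or whether it restarts after an earlier CE-COPD.

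Patients without CE-COPD get a proportion of days instead. Its formula counts days on which "albuterol use exceeded 4 inhalations/total number of eMDPI study days for a given patient", although the three thresholds listed beneath it are baseline-relative.

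SAP 7.2.2.1 tabulates flow values by CE-COPD status, by severity "and for the first occurrence of a single day increase of 20% from baseline use". SAP 7.3.2.1 does the same for total daily steps (TDS) and 7.4.2.1 for the sleep disruption index (SDI).

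On maxima, SAP 7.1.1 says: "For patients who experienced a CE-COPD, the maximum number of inhalations taken within a 24-hour period is determined among the days prior" to the symptom peak. SAP 7.1.2.5 then says: "Summary descriptive statistics of the maximum number of inhalations taken in a 24-hour period will be presented overall and by CE-COPD status". The other measures follow suit: "For patients who experienced a CE-COPD, the maximum change from baseline is the maximum change prior to the exacerbation" for flow, "the maximum change from baseline in TDS is the maximum change from baseline in TDS during the days prior to the exacerbation" for steps and "the maximum daily change from baseline is the change prior to the exacerbation" for sleep. No window is stated for patients without CE-COPD.

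**The concern.** A single as-needed day often exceeds a 7-day mean by 20%. If the clock starts at the first such day, however early, a patient whose peak falls late gets a long lead time simply because the peak is late. A table showing a lead of about five weeks would be read as early warning, which is the purpose of the study. Patients without CE-COPD get no comparable quantity that would expose the artefact. The flow, step and sleep rows at the first 20% day inherit the same date.

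The maxima have a different fault. A maximum grows with the number of days searched, and CE-COPD patients are searched over fewer days. A comparison by CE-COPD status therefore starts with a handicap against the group expected to use more.

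**Working it through.** **The plan's own figure.** The documents give no figure for lead time or for the maxima. The number of events that would supply lead times does reproduce: 360 patients x 1.095 per year (midpoint of 1.05 and 1.14) x 84/365.25 = 90.7, against the stated 91.

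**Inputs from the documents.** 84 days of follow-up; baseline as the mean of days 1 to 7; three thresholds; Poisson daily counts with patient-specific means, the SAP's own model in 7.1.2.3.

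**Assumed, because the documents give no usage level, variability or event timing.** Mean use 0.5, 1, 2, 4 or 8/day; variance/mean 0.25, 1 or 2 (15 settings); lognormal patient effects (log-SD 0.5); peak uniform on days 8 to 84; true rise 0, 2 or 4/day over the last 5 days; search from day 8 to the day before the peak. Patients with zero baseline were dropped at 20%. Each setting had 40,000 simulated patients.

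**By hand.** Take Poisson use with mean 4 and baseline exactly 4. The 20% threshold is 4.8, so a day counts if use is 5 or more.
- P(5 or more) = 1 - e^-4 (1 + 4 + 8 + 10.667 + 10.667) = 1 - 0.629 = 0.371.
- Crossed by day 9: 1 - 0.629^2 = 0.60, so the median first crossing is study day 9.
- The median peak is day (8 + 84)/2 = 46. Subtracting 9 to 11 gives a lead of 37 to 35 days with no rise at all.

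**20% threshold, simulated.**
- No rise: 85-95% cross, first crossing at median day 9-11, median lead 34-38 days, R2 with study day of peak 0.82-0.97.
- True 5-day rise: median lead 30-37 days, R2 0.76-0.97.
- A second run (Poisson, peaks on days 15-84, 7-day rise) gave 38-39 days with and without a rise. Without a rise, searching from day 1 gave 46-47 days.

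**Very regular use.** With a true rise, the median lead falls to 13-25 days at variance/mean 0.1 and to 5-10 at 0.05. At a fixed 4/day with a 7-day rise it is 7 days, R2 0, which is correct.

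**Absolute thresholds, true 5-day rise, median lead in days.**

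| Threshold | variance/mean 0.25 | Poisson | variance/mean 2 |
|---|---|---|---|
| +2 (rise 2 or 4/day) | 5 at means 0.5-4; 21-23 at 8 | 5, 13-15, 25-27, 32, 35 at means 0.5, 1, 2, 4, 8 | 19-36 |
| +4 (rise 4/day) | 5 at all means | 4-5 up to mean 2; 10 at 4; 25 at 8 | 5 up to mean 1; 18, 27, 33 at 2, 4, 8 |

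**A look-back limit alone.** With a 14-day limit and the second run's assumptions, 92-97% of patients still cross 20% with no rise. The median lead is 12-13 of 14 days, with or without a rise.

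**Formula for patients without CE-COPD.** For an illustrative baseline of 6/day, the three thresholds are 6 x 1.2 = 7.2, 6 + 2 = 8 and 6 + 4 = 10. The printed formula counts every day with 5 or more, including days below baseline.

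**Maxima.** With the peak at the median day 46, 45 days are searched, against 84 in patients without an event (assumed, as no window is stated). Differences are CE-COPD minus none, in inhalations; daily counts stand in for rolling 24-hour counts.

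| True rise | As planned | Equal 14-day windows |
|---|---|---|
| None | -0.1 to -1.9 | 0.0 |
| 2/day | -1.2 to +2.1 (negative in 4 of 15 settings) | +1.3 to +2.8 |
| 4/day | 0.0 to +4.4 | +3.1 to +5.6 |

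A generic normal measure standing in for flow, steps and sleep, identical in both groups, has a maximum change 0.3-0.5 within-patient SD smaller in CE-COPD patients.

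**The case against.** The strongest reply is that the size rests on assumed variability. Inclusion criterion g moves maintenance as well as rescue SABA onto the study inhaler, so some patients may dose very regularly, and for them the rule can work. Uniform peaks are also an assumption. This stands: a reader might infer a five-week lead whether or not use rises, but the documents give no within-patient variance and do not support that as an unconditional statement.

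A reader might also infer that the flow, step and sleep analyses miss the run-up to the event. They do not. SAP 7.2.2.1, 7.3.2.1 and 7.4.2.1 already summarise these measures at 1, 3, 5, 7, 10, 14 and 21 days before the peak. The first-20%-day rows are supplementary.

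The formula may be a drafting slip rather than a considered rule, and a corrected proportion of days would give readers a useful background crossing rate. Even so, a programmer cannot implement both the formula and the thresholds.

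Cutting maxima at the event has a reason: it keeps out use caused by the exacerbation. The resulting bias runs against the study hypothesis. With a rise of 2/day it reverses the sign in only 4 of 15 settings (variance/mean 2 at means 2, 4 and 8; Poisson at mean 8), and with a rise of 4/day in none. That justifies the cut in CE-COPD patients, but not the unequal windows.

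Finally, these are descriptive tables in an exploratory study without multiplicity control. That limits the consequence but does not make the lead time interpretable.

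**Conclusion.** The point holds with conditions. If daily use varies at least moderately (variance/mean 0.25 or more) and peaks are spread evenly over days 8 to 84, the 20% lead time is mainly the peak's study day minus about 9 to 11. Its median is then roughly 30 to 38 days and barely responds to a true 5-day rise. At variance/mean 0.1 or less the artefact shrinks or disappears. The +2 and +4 thresholds are affected mainly in variable or heavy users.

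The formula mismatch and the unequal windows are visible in the text without any assumption. The size of the maxima bias, about 0.1 to 1.9 inhalations with no true difference, does depend on the assumed usage and event timing.

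It would be wrong to conclude that the study's main test is compromised. The fixed-window analyses in SAP 7.1.2.2, 7.1.2.3 and 7.5.2.1, the forward 7-day analysis in 7.5.2.2 and the fixed-day flow, step and sleep summaries do not share the fault. The change is worth making because the timing of the rise is a named parameter and, as defined, may say little about timing.

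**What to change.** (a) **Maxima.** Compute all maxima over equal-length windows, for example the 14 days before the symptom peak in CE-COPD patients. In the others, use the same window before an index day drawn from the CE-COPD patients' peak study days. Shorten the windows in both groups for early events. State whether maximum change means a rise or a fall.

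(b) **Timing of the rise.** Replace the first-ever crossing, or at minimum accompany it, with the proportion of patients at or above each threshold on each of days 14 (or 21) to 1 before the peak. Set these beside the matched index windows, with the difference and 95% CI. Drop the first-20%-day rows for flow, steps and sleep, or add the index-window comparison to the existing fixed-day summaries.

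Do not define lead time formally as a run of days with the lower confidence limit above zero, because its length depends on sample size. If such a run is shown, label it exploratory and give it overall only. Severe events number about 13 (14% of 91; the plan prints 14). With 13 CE-COPD patients against 280 without and a true 5-day rise of 2/day (means 2-8, variance/mean 1-2), the median run at 20% and +2 was 0 to 4 days, and 15-74% of simulated trials showed none. Note also that higher usual use in CE-COPD patients can produce spurious differences. At 1.5 to 2 times the use with no rise, a spurious run appeared in 9-31% of trials at +2, 0-32% at +4 and at most 8% at 20%. The retrospective reliever-use study described in Protocol 3.3 makes such a difference plausible.

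(c) **Formula.** Correct the proportion in SAP 7.1.2.4 to count days at or above each of the three stated thresholds.

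Cost: SAP wording and programming, no new data. Rises earlier than the window are missed, early events have short windows, and if the first crossing is replaced, timing becomes a group-level rather than a patient-level result.

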7.1.1. Albuterol Use Definition

Baseline albuterol use is defined as the mean number of inhalations per day from day 1 to day 7. If no inhalations were taken during study day 1 through study day 7, the ‘baseline inhalation’ is the first available inhalation after study day 7. For analyses relative to baseline albuterol use, patients who had a CE-COPD during study day 1 through study day 7 will be excluded.

Week 1 Patient Albuterol Use: Week 1 patient albuterol use is each patient’s total number of albuterol inhalations taken and the number of days used during the first week (study day 1 through study day 7) of study participation with an indicator of whether or not the most frequent daily usage of albuterol is in 1 of the following 3 categories: (a) 0 to 2 inhalations, (b) 3-6 inhalations and (c) > 6 inhalations. It is presented as WK1:I#iD#dMTN#n, where “i” is the number of albuterol inhalations and “d” is the number of days used in the first 7 days of the study, and “n” is an indicator of whether or not the most frequent daily usage of albuterol falls into one of the 3 categories. If there is a tie in the most frequent daily usage, the category with the highest number of inhalations will be reported. For example, “I28D7MTN2” indicates a total of 28 inhalations were taken, albuterol use was used each of the 7 days and the highest most frequent usage per day falls into category 2 with 3-6 inhalations.

Week 2 Patient Albuterol Use: Week 2 patient albuterol use is each patient’s total number of albuterol inhalations taken and the number of days used during the second week (study day 8 through study day 14) of study participation with an indicator of whether or not the most frequent daily usage of albuterol is in one of the following 3 categories: (a) 0 to 2 inhalations, (b) 3-6 inhalations and (c) > 6 inhalations. It is presented as “WK2:I#iD#dMTN#n”, where “i” is the number of albuterol inhalations and “d” is the number of days used in the second week of study, and “n” is an indicator of whether or not the most frequent daily usage of albuterol is in one of the 3 categories. If there is a tie in the most frequent daily usage, the category with the highest number of inhalations will be reported.

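### SAP 7.1.2.4 promises day-frequencies for three increases over baseline in patients without a CE-COPD, but its only formula counts days above 4 inhalations in absolute terms

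*SAP*

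**What the plan says.** SAP 7.1.1 sets the reference: "Baseline albuterol use is defined as the mean number of inhalations per day from day 1 to day 7".

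SAP 7.1.2.4 has two parts. For patients with a CE-COPD it summarizes the number of days before the symptom peak when use increased, on three thresholds relative to baseline. The first is "First occurrence of a single day increase of 20% from baseline use prior to CE-COPD"; the others are absolute rises of 2 and 4 inhalations.

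For the remaining patients the measure changes: "Among patients who did not experience a CE-COPD, summary statistics, including 95% CIs intervals of the proportion of eMDPI time on study days" on which a threshold was exceeded. A parenthesis in the same sentence defines the ratio as the number of days on which a single day's "albuterol use exceeded 4 inhalations/total number of eMDPI study days for a given patient". The sentence then says that the result "will be summarized for 3 thresholds defining an increase in albuterol use" and lists them:

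- "First occurrence of a single day increase of 20% from baseline use"
- "First occurrence of a single day absolute increase of 2 inhalations from baseline use"
- "First occurrence of a single day absolute increase of 4 inhalations from baseline use"

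Neither the rest of the SAP nor its table of changes from the protocol (section 20) reconciles the parenthesis with the list.

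**The concern.** The formula and the list describe different quantities. The list is relative to each patient's baseline; the formula is an absolute level. One fixed numerator cannot produce three summaries. A first occurrence happens at most once per patient, so it suits the days-to-peak measure used for CE-COPD patients but not a proportion of days.

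The study hypothesis is that albuterol use rises before a CE-COPD and can mark deterioration. To judge such a marker one needs to know how often the same rise occurs in patients who have no event. Section 7.1.2.4 is the only place where day-frequencies of the +20%, +2 and +4 rises are to be reported for those patients. If the absolute count is programmed, the table will describe how heavily patients use the inhaler while being labelled as increases.

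**Working it through.** The SAP gives no numerical result for this summary, so there is no figure to reproduce. The check applies the written numerator and the three listed thresholds to the same patient, whose use has not changed from baseline b.

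**Inputs from the documents.** Numerator: more than 4 inhalations, so at least 5 whole inhalations (SAP 7.1.2.4). Thresholds: (i) 1.2 × b, (ii) b + 2, (iii) b + 4 (SAP 7.1.2.4). Baseline: mean per day over days 1 to 7 (SAP 7.1.1). Follow-up: 12 weeks × 7 = 84 days. Steady use of 5 or more a day is compatible with the regimen in SAP 2.1.1.3: 1 to 2 inhalations every 4 hours as needed allows up to 2 × 6 = 12 a day.

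**Inputs assumed.** The values of b; Poisson daily counts with constant mean b in the second check; baseline equal to b without sampling error; thresholds read as at least.

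**Check 1, no variation.** If use equals b every day, (i) needs b ≥ 1.2b, (ii) needs b ≥ b + 2 and (iii) needs b ≥ b + 4. All three fail for any b above 0, so each proportion is 0%. The written numerator needs only b ≥ 5 and then gives 100%. No distribution is assumed.

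**Check 2, stable Poisson use.** The probability that a day is counted is P(X ≥ k) = 1 − Σ(x<k) e^(−b) b^x / x!, where k is the smallest whole count that meets the rule. For b = 2 and the written numerator, k = 5: 1 − e^(−2)(1 + 2 + 2 + 1.333 + 0.667) = 1 − 0.1353 × 7 = 0.053.

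| b per day | k: written, (i), (ii), (iii) | Written (>4) | (i) +20% | (ii) +2 | (iii) +4 |
|---|---|---|---|---|---|
| 2 | 5, 3, 4, 6 | 5.3% | 32.3% | 14.3% | 1.7% |
| 5 | 5, 6, 7, 9 | 56.0% | 38.4% | 23.8% | 6.8% |
| 6 | 5, 8, 8, 10 | 71.5% | 25.6% | 25.6% | 8.4% |
| 8 | 5, 10, 10, 12 | 90.0% | 28.3% | 28.3% | 11.2% |

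Over 84 days, a stable user of 8 a day is counted on about 76 days by the formula, against about 24, 24 and 9 under (i), (ii) and (iii).

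**Sensitivity to strict bounds.** If the thresholds must be exceeded, (i), (ii) and (iii) become 25.6%, 15.3% and 4.3% at 6 a day, and 28.3%, 18.4% and 6.4% at 8 a day. The gap from the written numerator widens. At 2 a day they become 32.3%, 5.3% and 0.5%, so (ii) then coincides with the written rule.

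**Where the rules coincide.** With inclusive bounds, at least 5 equals (i) only for 3.33 < b ≤ 4.17, (ii) only for 2 < b ≤ 3, and (iii) only for 0 < b ≤ 1. As a general definition it is none of the three.

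**Light users.** A patient with baseline 1 who takes 4 in a day (+3, or +300%) meets (i) and (ii) but is not counted by the formula.

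**The case against.** The strongest reply is that this is a drafting residue. The sentence speaks of exceeding a given threshold and promises results for three, so a programmer could not produce the table from a single count and would either ask or substitute each threshold. That is plausible, and it makes the consequence conditional. A reader might infer that steady heavy users will in fact be reported as increasing on most days; the text supports only that they would be if the formula is followed. It does not remove the fault. The parenthesis is not marked as an example, and SAP 7.1.2.1 uses the same construction with an explicit baseline-relative numerator that is plainly meant to be followed.

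A reader might also infer that the SAP has no other information on threshold crossings without an exacerbation. That goes too far. SAP 7.1.2.1 reports, by CE-COPD status, the share of days on which use was not above the baseline average; its complement is a baseline-relative crossing frequency in both groups. SAP 7.5.2.2 follows patients for 7 days after the first day above 4, 8 or 12 inhalations. Neither covers the +20%, +2 and +4 rises as day-frequencies.

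Nor is the use of different measures in the two groups an error in itself. Days before the peak is a parameter named in the protocol and has no meaning for a patient without a peak. Finally, the summary is descriptive, in an exploratory study, and no test, sample size or decision rule rests on it. All of that stands and limits the importance of the point.

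**Conclusion.** The definition is internally inconsistent and should be corrected. If followed as written it replaces increase with level of use: 100% against 0% on every threshold for a patient constant at 5 or more a day, a result that needs no distributional assumption. With day-to-day variation the formula overstates at 6 and 8 a day and, at 2 a day, understates against +20% and +2 (inclusive bounds). Those percentages rest on Poisson counts, illustrative means and a baseline treated as known rather than as a 7-day average. Because the documents do not give the distribution of baseline use, the number of patients affected cannot be stated. The damage is confined to one descriptive summary, though it is the only one that gives these three frequencies in event-free patients.

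**What to change.** In the second part of SAP 7.1.2.4:

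- Replace the parenthesis with, for each threshold, the number of eMDPI study days meeting that increase over the patient's own baseline, divided by the patient's total eMDPI study days.
- Delete the first-occurrence wording from this list only.
- State whether the bounds are inclusive. The sentence speaks of exceeding a threshold, while the list describes a rise of a given size.
- Require use strictly above baseline. Otherwise a baseline of 0 makes 1.2 × 0 = 0 and every day without use counts as an increase. This matters because the ITT set includes patients who never use the inhaler, for whom SAP 7.1.1 leaves baseline undefined.
- State whether days 1 to 7, which define baseline, are in the denominator.
- If days above 4 inhalations are wanted, report them separately as an absolute level of use.

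The cost is SAP wording and three programmed numerators in place of one; no new data are needed. Reporting the same proportions for CE-COPD patients over their CE-COPD-free days before onset is an optional addition. It would allow a direct comparison, but those days mix genuine warning days with false alarms, and the correction does not depend on it.
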